Study Design	
Overall Study Design
 
This is an open-label, dose escalation study to evaluate the safety, PK, biodistribution, dosimetry, and tumor targeting potential of SNA002 in patients with solid tumors.
 
This study will consist of Screening Period, Baseline Period, Study Period and Safety Follow-up Period. A signed and dated informed consent form will be obtained before any study-related procedures are performed. Collect CT/MRI/PET/CT results from subjects within one month before screening to obtain baseline tumor assessment. Eligible patients will be enrolled at least two days before the administration of study drug. The radiation dose for all dose groups at the time of administration should be ranged from 37 to 200MBq. Four dose levels of NOTA-SNA002 are planned: 0.1mg, 0.3mg, 0.5mg and 0.9mg. The final drug product administered to the patient is [⁶⁸Ga]Ga-NOTA-SNA002. Three to seven patients will be sequentially enrolled into each dose cohort. Patients will be administered a single dose of SNA002 over 1 minute as an intravenous bolus. Patients will be observed for 6±1h and 24±6h post infusion for infusion-related and other adverse reactions. In the first cohort of patients, whole body imaging will be acquired using PET/CT at 15±5 minutes, 60±10 minutes and 120±20 minutes post-injection. Before each imaging, the patients need to empty bladder as much as possible. Total-body PET-CT scans can be performed on 1-2 subjects in a certain dose group or each dose group, covering at least one of the aforementioned time points. In the subsequent cohorts,

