	
  
 Dose Levels (mg)	Number of patients	
   
 0.1	3-7	
  
	Dose Levels (mg)	Number of patients	0.1	3-7
Dose Levels (mg)	Number of patients				
0.1	3-7				

	0.3	3-7	
	0.5	3-7	
	0.9	3-7	

Dose escalation criteria

Since SNA002 contains a PD-L1 nanobody that cannot block the binding of PD-1 to its ligands and the dose of PD-L1 antibody is extremely low, the main safety risk is likely to be occurrence of infusion-related reactions (IRRs), which are medically manageable. The dose escalation criteria will include image quality criteria and safety criteria (e.g., serious adverse events, Grade 2 or higher adverse events) as described below.

PD-L1 expression will be measured using immunohistochemistry [(IHC); 22C3-IHC assay] by obtaining at least one biopsy of a target lesion that is amenable to aspiration biopsy on Day 2. IHC results will be reviewed by the IRC. The correspondence between the IHC assay results and the PET imaging results will be evaluated by the IRC.

Dose-Escalation Rules

The dose escalation is determined through both imaging results and safety results:

- 1) **Imaging:** If the first three positive tumor lesions in a certain dose group judged by the IRC to having a high image quality (such as $T/B > 1.5$, etc.), it can be decided from the imaging perspective to increase to the next dose group after continuing to enroll 3-4 cases in this dose group, or directly increase to the next dose group for further exploration;
 - If the quality of the first 3 cases in the subsequent dose group is comparable to that in the previous dose group, the IRC shall discuss whether to discontinue further enrollment from a imaging perspective (e.g. The image quality of the first 3 cases in the 0.3mg dose group is similar to that in the 0.1mg dose group, then stop recruiting, and the 0.1mg dose was identified as the optimal image dose).

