5.1 Inclusion criteria

Patients must meet all the following criteria to be eligible for participation in this study:

- 1) Male or female patients, 18-75 years of age, inclusive.
- 2) Willing and able to provide signed and dated informed consent prior to any study-related procedures and willing and able to comply with all study procedures.

- 3) Histologically or cytologically confirmed solid tumors including but not limited to non-small cell lung cancer, breast cancer, esophageal cancer, head and neck carcinoma, ovary cancer and melanoma (with or without metastasis); Patients are allowed to enter the study at first diagnosis, at relapse or under treatment.
- 4) Obtain pathological results within one year.
- 5) Patients with the imaging results showing at least 1 tumor lesion that can be sampled by biopsy (enhanced CT, enhanced MRI or ^{18}F -FDG PET/CT results are acceptable).
- 6) ECOG PS 0-2 (See [Appendix 1](#) for details).
- 7) Adequate hepatic function as evidenced by meeting all the following requirements:
 - a) Total bilirubin (TBIL) $\leq 2.5 \times \text{ULN}$.
 - b) Aspartate aminotransferase (AST) and alanine aminotransferase (ALT) $\leq 3 \times \text{ULN}$.
- 8) Serum creatinine $< 1.5 \times \text{ULN}$ and blood urea nitrogen (BUN) $\leq 1.5 \times \text{ULN}$.
- 9) Adequate hematological function defined as:
 - a) White blood cell $3.0-10.0 \times 10^9/\text{L}$ in prior to study entry
 - b) Absolute neutrophil count $1.5-7.0 \times 10^9/\text{L}$ without growth factor support in prior to study entry
 - c) Hemoglobin $\geq 90\text{g/L}$ without transfusion in prior to study entry
 - d) Platelet count $75-300 \times 10^9/\text{L}$ without transfusion in prior to study entry
- 10) Coagulation tests, defined by the following:
 - a) Activated partial thromboplastin time (PTT) $\leq 1.5 \times \text{ULN}$
 - b) International normalized ratio (INR) $\leq 1.5 \times \text{ULN}$.
- 11) Blood pressure value $<$ grade 1 hypertension (including patients with a history of hypertension whose systolic blood pressure is $< 140 \text{ mmHg}$ and diastolic blood pressure is $< 90 \text{ mmHg}$ after exercise or drug treatment).
- 12) Baseline heart rate 60-100/minute (inclusive)

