7.3.2 Baseline Period

D-1

- 1) Review compliance with inclusion/exclusion criteria for the second time
- 2) Enrollment (Subjects can be enrolled in the relevant department due to primary tumor before D-1 and after D1 and complete the trial period during hospitalization) .
- 3) Record concomitant medications.

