8) Develop a plan for obtaining target lesion specimens (if applicable): Determine whether to collect tissue specimens after administration based on specific circumstances. If the subject has obtained a biopsy specimen within 2 weeks prior to enrollment and has obtained/can undergo immunohistochemical PD-L1 detection results (such as PD-L1 immunohistochemical detection of pathological tissues in different directions of the lesion collected through bronchoscopy within 2 weeks prior to enrollment), and no treatment has been given, no further biopsy is required. Otherwise, pathological specimens need to be collected in this clinical study. The collection method can accept biopsy or surgical resection of specimens, which is determined by the investigators based on the subject's situation.
 (note: the investigators can arrange for the subjects to enter a safe follow-up period after the subjects complete the tissue specimen collection (D2) or surgical specimen collection (D2-D5) during the trial period, or after the subjects who do not need to collect tissue specimens again complete all operations in D1, in order to shorten the waiting time for subsequent treatment from an ethical perspective).

9) Vital signs: Vital signs are evaluated at 6 ± 1 h after administration on D1.

10) Examination of injection site: observe injection site for redness, swelling, heat, pain, itching and other symptoms 6 ± 1 h after administration.

11) Record concomitant medications.

12) Record AEs.

D2 to D5

- 1) Target lesion specimen acquisition: Biopsy specimens can include endoscopic (such as gastroscopy, fiberoptic bronchoscopy, laparoscopy, etc.) and puncture biopsy specimens, which are generally conducted in D2. The preferred specimen for collection is the primary tumor lesion or metastatic lesion with the highest SUVmax; The collection principle is to collect at least one biopsy sample from the target tumor lesions that can be collected, and the maximum number of samples for the same patient is 5. Ideally, biopsies should be performed on both positive and negative lesions of the same patient under PET imaging. The location of specimen collection and the selected collection method will be determined by the investigators based on previous imaging results and the PET results of this experiment. Perform PD-L1 immunohistochemical detection after obtaining target tissue samples.

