7.3.7 Schedule of Events Table

Table 4 Schedule of Events Table

Study Period/Visits	Screening Period	Baseline Period	Study Period (5 days)		Safety Follow-up Period (D6-28)		Premature Withdrawal ¹⁸
Study Day (s)	D-14~2	D-1	D1	D2~D5	D6±1d	D28±2d	
Informed consent	x						
Inclusion/exclusion criteria	x	x					

Study Period/Visits	Screening Period	Baseline Period	Study Period (5 days)		Safety Follow-up Period (D6-28)		Premature Withdrawal ¹⁸
Study Day (s)	D-14~2	D-1	D1	D2~D5	D6±1d	D28±2d	
Demographics	x						
Physical examination	x			x			
Vital signs ¹	x		x	x			x
Medical history:	Personal history	x					
	Past history	x					
	Allergy history	x					
	Tumor History	x					
Tumor stage	x						
Pathological examination ²	x						
Laboratory examination ³	Blood routine	x			x		x
	Blood Biochemistry	x			x		x
	Electrolyte	x			x		x
	Thyroid Function	x					
	Coagulation Function	x			x		x
	Urinalysis	x					
	Blood Pregnancy (If Needed)	x					
	Serum Virology	x					
12-lead ECG	x				x		x
Cardiac function score	x						
Physical condition score	x						
Chest X-ray (can be ignored if there is chest CT) ⁴	x						
CT/MRI/PET-CT ⁵	x						
Administration							
[⁶⁸ Ga]Ga-NOTA-SNA002 administration ⁶			x				
Biological Samples, Imaging, Safety Data, Specimen Collection							
Blood sampling ⁷			x				
Urine sampling ⁸			x				
Ada ⁹			x		x	x	x
Pet-ct ¹⁰			x				
Measurement of radiation dose ¹¹			x				
Formulate a Plan for Obtaining Target Lesion Specimens (If Performed) ¹²			x				
Collection of tissue samples from target lesions (if performed) ¹³				x			
Pd-111 immunohistochemical examination ¹⁴	x			x			
Other							
Examination of injection site ¹⁵			x	x			
Enrollment ¹⁶		x					
Out of group						x	
Concomitant medications ¹⁷	x	x	x	x	x		x

Study Period/Visits	Screening Period	Baseline Period	Study Period (5 days)		Safety Follow-up Period (D6-28)		Premature Withdrawal ¹⁸
Study Day (s)	D-14~2	D-1	D1	D2~D5	D6±1d	D28±2d	
Ac ¹⁸			x	x		x	x
Distribute/recycle journal cards						x	

1. Vital Signs: tested during the screening period, 6 ± 1 hours after D1 administration, and 6 ± 2 hours after D2 biopsy (if performed).
2. Pathological Examination: if the pathological examination results within one year before screening are obtained, and the subject receives biopsy samples within two weeks before enrollment and has not undergone chemotherapy, radiotherapy, or immunotherapy until enrollment, biopsy may not be performed after administration in this clinical trial.

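### No vital signs are scheduled on D-1, on D1 before dosing or in the first 5 h after it, so the 6±1 h reading has no dosing-day baseline and early, transient, symptom-free changes have no planned record

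*Combined protocol and SAP*

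**What the plan says.** **Risk.** Under the dose escalation criteria, the Protocol Summary states that "the main safety risk is likely to be occurrence of infusion-related reactions (IRRs), which are medically manageable". Section 2.2, Table 3 instead puts radiation exposure first. Section 6.1.7.1 reports a possible infusion reaction as the only toxicity in the 2-week monkey study, seen after three intravenous doses.

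**Measurement.** Section 10.4.4 lists blood pressure, pulse, respiration and body temperature as safety indicators. The D1 list in section 7.3.3 has one entry, "Vital signs: Vital signs are evaluated at" 6±1 h after administration. Note 1 to Table 4 agrees: "Vital Signs: tested during the screening period", then 6±1 h after the D1 dose, then 6±2 h after a D2 biopsy if one is done. Section 7.3.5 adds a reading at early termination.

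**D-1.** Section 7.3.2 lists three items. The first is "Review compliance with inclusion/exclusion criteria for the second time"; the others are enrolment and concomitant medication. The criteria include blood pressure below 140/90 mmHg and heart rate 60-100 per minute (section 5.1), but no new measurement is listed.

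**Biopsy.** For a patient with a recent specimen, an available PD-L1 result and no treatment since, section 7.3.3 says that "no further biopsy is required".

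**Observation.** The Protocol Summary also says: "Patients will be observed for 6±1h and 24±6h post infusion for infusion-related and other adverse reactions". It gives no parameters or measurement times for that observation.

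**The concern.** Safety and tolerability is a primary objective of this first-in-human study. The reaction that the protocol expects would follow an injection lasting about 1 minute, yet the first scheduled vital signs come at least 5 h later. The value against which they would be read was taken at screening. Between the two, the patient may have had antihistamines or antipyretics 30-60 min before injection (section 7.5), has drunk at least 500 mL of water (section 7.3.3), and may be under treatment for the tumour (section 5.1). An unusual 6 h value therefore cannot be separated, from scheduled data alone, from a shift that was present before the injection. Readings not taken on D1 cannot be recovered later, and the planned sample is only 12-28 patients.

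**Working it through.** **1. The plan's own figure.** Four dose levels with 3 to 7 patients each: 4 × 3 = 12 and 4 × 7 = 28. This reproduces the stated 12-28.

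**2. Scheduled vital signs, text against table.**

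| Time | Scheduled? | Source |
|---|---|---|
| D-14 to D-2 | Yes | 7.3.1, Table 4 |
| D-1 | No | 7.3.2, Table 4 |
| D1, before injection | No | 7.3.3, Table 4 note 1 |
| D1, 0 to 5 h | No | 7.3.3, Table 4 note 1 |
| D1, 6±1 h | Yes | 7.3.3, Table 4 note 1 |
| 6±2 h after biopsy | Only if performed | 7.3.3, Table 4 note 1 |
| D6±1 and D28±2 | No | 7.3.4, Table 4 |
| Early withdrawal | Yes | 7.3.5, Table 4 |

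Text and table agree, so this is the plan and not a slip in one place.

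**3. Length of the gap.** Earliest post-dose reading: 6 − 1 = 5 h (300 min). Latest: 6 + 1 = 7 h (420 min).

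**4. Age of the comparator.** D-14 to D-2 is 14 to 2 days before D1 if there is no Day 0, and 15 to 3 days if there is one. The documents do not say which.

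**5. Readings per completer.** Without a new biopsy: screening + 6±1 h = 2. With one: 3.

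**6. Existing contacts inside the gap.** Seven post-dose blood draws (the last by 150 + 10 = 160 min), three scans (starting at 10-20, 50-70 and 100-140 min), two urine collections (by 210 min) and an ambient dose reading (210-270 min). A reading could be attached to one of these without a new visit.

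**7. What lacks a planned record.**
- Early change with symptoms: recorded as an adverse event (7.3.3; Table 4 note on AEs; 8.4.1).
- Symptom-free change lasting to 5-7 h: caught by the existing reading.
- Early, transient, symptom-free change: no planned record.

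**8. Risk context.** The top dose is 0.01503 mg/kg, and the NOAEL-based human equivalent doses are 0.16 (female) and 0.48 mg/kg (male). Margins: 0.16/0.01503 = 10.6 and 0.48/0.01503 = 31.9. The per-kg figure implies a body weight of 0.9/0.01503 = 59.9 kg.

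**9. Which contacts suit a reading.** Activity remaining by decay alone is 2^(−t/68), with t in minutes and the 68 min half-life from section 6.1.2.
- *Between the 5 and 10 min draws.* The draws fall at 4-6 and 9-11 min, so the interval is 9 − 6 = 3 to 11 − 4 = 7 min. It is shared with preparation for scan 1: "Before each imaging, the patients need to empty bladder as much as possible". At 6 min, 94% of activity remains. This slot is too crowded.
- *At the 30 min draw (28-32 min).* 2^(−30/68) = 74%. Scan 1 starts at 10-20 min. If it lasts 15-30 min (an assumption inferred from exclusion criterion 16), it ends at 25-50 min and may still be running, so the reading needs an alternative at scan end. At 50 min, 60% remains.
- *At the 150 min draw.* 2^(−150/68) = 22%. This slot is feasible but adds less about early change.

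**10. Volume of the fix.** Two added sets: 2 × 12 = 24 to 2 × 28 = 56. Per completer, 2 becomes 4 (3 becomes 5 with a biopsy).

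**The case against.** The strongest reply is that the gap is in the schedule rather than in patient care. The observation sentence in the Protocol Summary may mean continuous watching for 6±1 h. Staff meet the patient repeatedly up to 160 min. Adverse events include signs as well as symptoms (8.1.1), and investigators must observe and treat them and keep original records (8.4.1). The D-1 eligibility review could reasonably prompt a fresh blood pressure and heart rate, and inpatients may have ward readings. Dose margins are wide, a single dose is given, and the monkey finding was only a potential reaction.

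All of this stands and limits the size of the point. None of it schedules a reading, names a parameter or makes a dosing-day value available for analysis. Site procedures may add readings, but the documents require none.

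Three stronger inferences are tempting and are not supported:
- *Infusion reactions would go unrecorded.* Symptomatic ones are recorded and treated.
- *There is no baseline.* There is one, at screening, bounded by the eligibility limits. What is missing is a scheduled dosing-day value.
- *The safety results or escalation decisions are biased.* Escalation stops on graded or serious adverse reactions (6.1.7.2). Section 8.2.1 sets no vital-sign thresholds, and an untreated, symptom-free change would count as mild there.

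**Conclusion.** The point holds in a narrow form. A listed safety indicator has no scheduled reading on D-1, before dosing on D1 or in the first 300 min after injection. Its one routine post-dose value has a scheduled comparator 2-14 days old (3-15 if a Day 0 is counted). Only changes that are early, transient and symptom-free lack a planned record.

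This rests on the D1 text and Table 4 being the complete schedule, and on no unlisted measurement being required by the D-1 review. No endpoint, bias or decision is shown to change. The gain is a fuller description of early safety in a small first-in-human sample. Low priority, but worth doing because it is cheap.

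**What to change.** In section 7.3.3 and Table 4 note 1, add two sets of vital signs:

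1. With the pre-dose blood sample, within 30 min before injection, designated as the D1 baseline. Record any premedication and the fluid intake, because permitted premedication (30-60 min before injection) will already have been given.
2. At the 30 min draw, or as soon as the first scan ends if it is still running. Tie it to the draw and not to a scan time, because imaging times may change after the first cohort.

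Keep the 6±1 h reading. A set at the 150 min draw is optional. Do not add one between the 5 and 10 min draws, where it would compete with the ±1 min PK sampling and bladder emptying.

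**Cost.** One line of text, one table note and two sets of eCRF fields; no new visit. It takes a few minutes per patient and slightly raises staff exposure at the 30 min reading. An automatic cuff would limit close contact.

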2.1 Background Information

Epidemiology

Cancer is the second leading cause of death worldwide, accounting for about 1 in every 6 deaths. In 2018, there were an estimated 17.0 million cases of cancer diagnosed and 9.6 million cancer deaths around the world (WHO, 2018). By 2040, the global burden is expected to reach 27.5 million new cancer cases and 16.3 million cancer deaths (American Cancer Society, 2018). To date, the conventional therapies for patients with advanced solid tumors include palliative surgery, chemotherapy, radiotherapy, and more recently immunotherapy has been added to the repertoire.^[1]

Table 1 First five incidence and Mortality of Common Cancers in China and America in 2020

(approximate)

China	Incidence	Lung (820,000)	Colon (550,000)	Gastric (480,000)	Breast (420,000)	Liver (410,000)
	Mortality	Lung (710,000)	Liver (390,000)	Gastric (370,000)	Esophagus (300,000)	Colon (280,000)
American	Incidence	Breast (280,000)	Lung (250,000)	Prostate (240,000)	Colon (170,000)	Bladder (90,000)
	Mortality	Lung (160,000)	Colon (60,000)	Breast (50,000)	Pancreatic (50,000)	Prostate (40,000)

PD-L1 is expressed in many cancers, including bladder, breast, colon, cervical, pancreatic, gastric, and non-small cell lung cancer (NSCLC) as well as melanoma and malignant glioma (Freeman et al 2000).

There are currently 6 PD-(L)1 monoclonal antibodies approved for various cancers in the U.S. Some indications are limited to tumors that are known to express PD-(L)1 while others include

patients regardless of tumor PD-(L)1 expression status. Approximately 20-40% of cancer patients derive clinical benefit from PD-(L)1-targeting mAbs. The efficacy of these mAbs can vary greatly (16–100%) among individual patients. In addition, some studies have reported substantially improved efficacy when used for the treatment of tumors with high PD-(L)1 expression (Walker et al., 2016. Guo et al., 2020. Bensch et al., 2018) . Screening patients for PD-(L)1 expression may be helpful in guiding treatment decisions for patients with certain tumor types at initial diagnosis or at recurrence.

Nuclear medicine and molecular tracing technologies are effective measures for the early diagnosis of solid tumors and extent of disease. The use of radioactive molecular probes allows detection and evaluation of PD-1 and PD-L1 expression in solid tumors, distant metastases, and throughout the body. Unlike immunohistochemistry (IHC) methods for establishing PD-(L)1 expression, radiolabeled PD-(L)1 antibodies offer a noninvasive method (i.e., no biopsy required) of assessing PD-(L)1 expression status and can measure changes in expression during treatment. This technique may therefore serve as an improved strategy for screening and selection of PD-(L)1 responders, optimization of anti-PD-(L)1 regimens, and evaluation of patient prognosis.

Similar products in development

There is currently no PD-L1 imaging agent available in any country. However, several radiolabeled PD-L1 mABs are undergoing clinical evaluation, and these are listed below.

Table 2 List of PD-L1 imaging drug

Product	Study site	Phase	Molecular Type	Molecular Size	Labeled nuclide	Half-life of nuclide	Optimum development time
⁸⁹ Zr-atezolizumab	University Medical Center Groningen	Phase I	Macromolecule monoclonal antibody	150 kDa	⁸⁹ Zr	78.4 h	7 d
¹⁸ F-BMS-986192	Cancer Center Amsterdam	-	adnectin	10 kDa	¹⁸ F	109.8 min	70-90 min
⁹⁹ mTc-NM-01	Shanghai General Hospital	Phase I	Single-domain antibody	15 kDa	⁹⁹ mTc	6 h	2 h
⁸⁹ Zr-KN035	The First Affiliated Hospital of Soochow University	Phase I	Single-domain antibody	80 kDa	⁸⁹ Zr	78.4 h	-
RGEN3504	Regeneron Pharmaceuticals Inc.	Phase I	-	-	⁸⁹ Zr	78.4 h	-
⁸⁹ Zr-avelumab	Radboud University Nijmegen	Phase I	Macromolecule monoclonal antibody	150 kDa	⁸⁹ Zr	78.4 h	-
⁸⁹ Zr-durvalumab	Radboud University Nijmegen	Phase I	Macromolecule monoclonal antibody	150 kDa	⁸⁹ Zr	78.4 h	-

2.1.1 ⁸⁹Zr-atezolizumab

⁸⁹Zr-atezolizumab is a macromolecule monoclonal antibody with a molecular weight of about 150

kDa. Its optimum development time is on D4–D7 after administration, and the maximum SUV_{\max} of the tumor is about 10. However, tumor SUV_{\max} is between 5 and 10 on D0–D4 after administration. PET imaging shows that the uptake of ^{89}Zr -atezolizumab is low in brain, subcutaneous tissues, muscle, and lungs, but high in liver and intestinal tract.

A study by de Vries et al. (van de Donk et al., 2020) examined the application of ^{89}Zr -atezolizumab in the evaluation of PD-L1 treatment efficacy in 25 patients with advanced or distant metastatic NSCLC, bladder cancer, or triple negative breast cancer. Twenty-two patients received 37 MBq ^{89}Zr -atezolizumab (1 mg atezolizumab) intravenously and were examined by PET imaging at 1 hour, 2 days, 4 days and 7 days after administration. Tumor SUV_{\max} and target to background ratios in the lungs and bone metastases were stable on D7, and SUV_{\max} was comparable on D4 and D7. High uptake of the imaging agent was observed in the tumor region, and the geometric mean of SUV_{\max} was 10.4 (1.6–46.1). IHC staining of tumor biopsy specimens (IHC kit SP142) showed that higher PD-L1 score was associated with higher ^{89}Zr -atezolizumab uptake in the tumor region (IHC scores of 0, 1, and 2 corresponded to a mean tumor SUV_{\max} of 9.2, 10.1, and 17.1, respectively). The mean SUV_{\max} of patients was significantly correlated with progression-free survival (PFS) and overall survival (OS). Only one drug-related adverse event (AE), mild pruritis, was observed among the 22 patients (van de Donk et al., 2020).

2.1.2 ^{18}F -BMS-986192

^{18}F -BMS-986192 is a small molecule adnectin-based imaging agent with a molecular weight of about 10 kDa. PET imaging at 70–90 min after administration showed that the mean tumor SUV_{\max} was 2.9 in patients with < 50% PD-L1 expression, and 8.2 in patients with > 50% PD-L1 expression. High uptake was observed in the bladder, kidneys, spleen, and liver, and low uptake was observed in bone marrow, lungs, and brain.

Niemeijer et al. (Niemeijer et al., 2018) investigated ^{18}F -BMS-986192 to assess PD-L1 expression in 13 advanced NSCLC patients receiving nivolumab. One patient received 65.5 MBq ^{18}F -BMS-986192, while the other 12 patients received $3 \pm 10\%$ MBq/kg ^{18}F -BMS-986192. Using the SUV value at 70–90 min after injection as a semi-quantitative readout, the SUV_{peak} of ^{18}F -BMS-986192 in the metastatic brain lesion was only 0.2–0.9, which may be attributed to the reduced permeability of imaging agent through the blood-brain barrier. Excluding the SUV of brain metastasis, IHC showed that the SUV_{peak} in patients with < 50% PD-L1 expression was lower (2.9) than that of patients with $\geq 50\%$ PD-L1 expression (8.2). After 3 months of nivolumab therapy, tumor SUV_{peak} was also lower in non-responders (median 3.2) as compared to responders (median 6.5). No grade 3 or greater drug-related AEs were observed among the 13 patients (Niemeijer et al., 2018).

2.1.3 $^{99\text{m}}\text{Tc}$ -NM-01

Xing et al. (Xing et al., 2019) reported on ^{99m}Tc -NM-01 use for the assessment of PD-L1 expression in 16 patients with NSCLC. The 16 patients received 3.8–10.4 MBq/kg of ^{99m}Tc -NM-01 (either 100 or 400 μg of NM-01) intravenously and underwent PET imaging at 10 min, 1 h, 2 h, 3 h, and 24 h after administration. PET imaging results at 2 h after administration showed that the tumor-to-lung (TL) and tumor-to-blood pool (TBP) ratios were higher at 2 h (2.69 and 2.22, respectively) than at 1 h after administration (2.22 and 1.79, respectively). The results of tumor IHC staining were consistent with the PET imaging, showing that the 2 h TBP was lower in patients with $\leq 1\%$ PD-L1 expression (1.89) than in patients with $\geq 1\%$ PD-L1 expression (2.49). No drug-related AEs were observed in all patients during the 7-day follow-up period (Xing et al., 2019). No imaging agent-related AEs were observed in all patients during the 7-day follow-up period. In addition, the symptoms of advanced NSCLC, such as coughing, dyspnea, and fatigue, were not exacerbated by the administration of the imaging agent.

Unmet clinical needs

As nuclear medicine enters into the molecular era, the application of molecular imaging probes has become a topic of active research. PET not only allows early identification and diagnosis of tumors, but also provides systemic imaging of advanced and metastatic tumors. The PD-1/PD-L1 signaling pathway has become one of the key targets of cancer immunotherapy in recent years. PD-1/PD-L1 expression levels in tumors may correlate with treatment response and affect prognosis. The development of a PD-1/PD-L1-based radioactive molecular probe is not only important for improved tumor diagnosis effectiveness, but it also offers a potential tool for noninvasive evaluation of tumor PD-1 and PD-L1 expression at diagnosis and during therapy. This may guide treatment regimen optimization and inform prognosis.

